## LIST OF ABBREVIATIONS

AME	absorption, metabolism, and excretion
AE	adverse event
ALT	alanine aminotransferase
AST	aspartate aminotransferase
AUC	area under the concentration-time curve
BMI	body mass index
CA	Competent Authority
CCMO	Centrale Commissie Mensgebonden Onderzoek (Central Committee on Research Involving Human Subjects)
CHMP	Committee for Medicinal Products for Human Use
GMP	Good Manufacturing Practice
CSP	clinical study protocol
CSR	clinical study report
CTCAE	Common Terminology Criteria for Adverse Events
CTD	Clinical Trial Directive
DprE1	decaprenylphosphoryl-β-D-ribose-2'-epimerase
ECG	electrocardiogram
eCRF	electronic case report form
EDS	Early Development Services
EMA	European Medicines Agency
FDA	Food and Drug Administration
GCP	Good Clinical Practice
GDPR	General Data Protection Regulation
HBsAg	hepatitis B surface antigen
HCV	hepatitis C virus
HED	human equivalent dose
HKI	Hans Knöll Institut
ICF	informed consent form
ICH	International Council for Harmonisation
IEC	Independent Ethics Committee
MEB	Medicine Evaluation Board
MedDRA	Medical Dictionary for Regulatory Activities
NOAEL	no observed adverse effect level
PCR	polymerase chain reaction
PK	pharmacokinetic(s)
PRA	PRA Health Sciences
SAE	serious adverse event
SAP	statistical analysis plan
SOP	standard operating procedure
SUSAR	suspected unexpected serious adverse reaction
TEAE	treatment-emergent adverse event
WMA	World Medical Association
WMO	Wet medisch-wetenschappelijk onderzoek met mensen (medical research involving human subjects act)

Note: Definitions of pharmacokinetic (PK) parameters are provided in Section [3.5.3](#).

## 1. INTRODUCTION

[figure not shown]
[figure not shown]
### 1.1 Background

[figure not shown]
[figure not shown]
[figure not shown]
BTZ-043 is a promising new antibiotic for the treatment of tuberculosis. Its mechanism of action is based on a reduction of BTZ-043 to a transient nitroso moiety, which then reacts with an essential cysteine residue in the enzyme decaprenylphosphoryl- $\beta$ -D-ribose-2'-epimerase (DprE1), forming a semimercaptal as covalent adduct. DprE1 itself is required for the biosynthesis of decaprenylphosphoryl- $\beta$ -D-arabinose, an essential component for the cell wall assembly of mycobacteria. Formation of the covalent adduct between BTZ-043 and DprE1 results in inhibition of cell wall biosynthesis and loss of viability of *M. tuberculosis*. Due to this mechanism BTZ-043 is highly selective for mycobacteria species (and some other members of Actinomycetales), but does not affect the gut flora.

In 2018 a Phase 1a study entitled “A Randomized, Double blind, Placebo-controlled, Single Ascending Dose Study to Evaluate Safety, Tolerability, and Pharmacokinetics (PK) of Single Doses of BTZ-043 in Healthy Adult Volunteers” (LMU-IMPH-BTZ-043-01) was conducted in humans and currently a Phase 1a/2b study entitled “A Prospective Phase 1b/2a, Active-controlled, Randomized, Open-label Study to Evaluate the Safety, Tolerability, Extended Early Bactericidal Activity and PK of Multiple Oral Doses of BTZ-043 Tablets in Subjects With Newly Diagnosed, Uncomplicated, Smear-positive, Drug-susceptible Pulmonary Tuberculosis” (PanACEA-BTZ-043-02) is ongoing. This human absorption, metabolism, and excretion study is conducted during Phase 2 proof of concept studies and before a Phase 3 study is initiated.

#### 1.1.1 Nonclinical Summary

##### Safety

A large rectangular area of the page has been completely blacked out, indicating a redaction of sensitive information.A second large rectangular area of the page has been completely blacked out, indicating a redaction of sensitive information.

Pharmacokinetics

**1.1.2 Clinical Summary****Safety**

[REDACTED]

[REDACTED]

[REDACTED]

## 1.2 Risk-benefit Assessment

There is no expected clinical benefit for the healthy subjects who will participate in this study. The information obtained in this study can be used for the further clinical development of BTZ-043. As depicted in [Table 2](#), BTZ-043 has been well tolerated in much higher exposures as proposed in this study.

Overall, on the basis of the available nonclinical and clinical data, the risk-benefit profile of BTZ-043 is judged acceptable for the proposed clinical study.

The risk-benefit assessment for the subjects receiving BTZ-043 remains unchanged in relation to the corona virus disease-19 (COVID-19) pandemic as available clinical and nonclinical results do not suggest that administration of BTZ-043 will lead to suppression or modulation of the immune system. In addition, the mode of action does not appear to have a substantial effect on the respiratory or cardiovascular system critically affected by a SARS-CoV-2 infection. As the subjects to be included in this study are in general young to middle aged without major comorbidities, the study population is not considered to be a high-risk population for serious COVID-19 disease. Only persons with a negative SARS-CoV-2 test at admission to the clinical research center will be allowed to participate in the study. In addition, all appropriate measures to prevent SARS-CoV-2 infection during the study will be taken as detailed in Section [3.2.1](#).

### 1.3 Study Rationale

This study will determine the disposition and metabolism of BTZ-043 in humans after oral administration. The use of radiolabeled molecules (usually [ $^{14}\text{C}$ ]) is a common method to ascertain information on the elimination routes and metabolic fate of a compound at an early stage of development. This evaluation will provide an estimate of PK parameters, the routes and rates of elimination of radioactivity, and identification of metabolites and metabolic pathways. These data will be compared with similar data obtained from nonclinical studies, both from PK and metabolic points of view. The rationale for the proposed dose can be found in Section [3.4.4](#).

## 2. OBJECTIVES

### 2.1 Primary

- To determine the rates and routes of excretion of [C]BTZ-043-related radioactivity, including mass balance of total drug-related radioactivity in urine and feces (and vomit, if applicable), following the oral administration of a single 500 mg dose of [C]BTZ-043 in healthy male volunteers.
- To determine the PK of total radioactivity in whole blood and in plasma.
- To characterize the plasma PK of BTZ-043 and main metabolites by liquid chromatography-mass spectrometry (LC-MS), if applicable.
- To characterize the urine concentrations of BTZ-043 and main metabolites by LC-MS, if applicable.

### 2.2 Secondary

- To assess the safety and tolerability of a single 500 mg oral dose of BTZ-043 administered to healthy male volunteers.

### 2.3 Exploratory

- To identify BTZ-043's metabolites in plasma, and to quantify metabolites not measured in the primary objectives by radiometry in order to elucidate key biotransformation pathways and clearance mechanisms of BTZ-043 in humans.
- To identify BTZ-043's metabolites in excreta (urine and feces) and to quantify metabolites not measured in the primary objectives by radiometry in order to elucidate key biotransformation pathways and clearance mechanisms of BTZ-043 in humans.

### 3. INVESTIGATIONAL PLAN

#### 3.1 Overall Study Design and Plan

##### 3.1.1 Type of Study

This will be a Phase 1, single-center, open-label, absorption, metabolism, and excretion (AME) study in 4 healthy adult male subjects.

##### 3.1.2 Screening Period

Subjects will report to the medical screening facility/clinical site for the eligibility screening (see Section 3.3 for inclusion and exclusion criteria) within 3 weeks prior to drug administration.

Subjects will sign the study-specific informed consent form (ICF) prior to any study-specific screening procedures being performed. The written informed consent will be obtained for all subjects, regardless of their eligibility for the study; the signed ICFs will be retained and archived at PRA Health Sciences (PRA) and a copy will be provided to the subject.

Eligibility screening will consist of the assessments as presented in the schedule of assessments ([Table 1](#)).

##### 3.1.3 Treatment Period

Subjects will be admitted to the clinical research center on Day -1, which is the day prior to Day 1, the day of drug administration.

Subjects will receive a single oral dose of 500 mg BTZ-043 containing 3.7 MBq of [C]BTZ-043 on Day 1. Subjects will be discharged from the clinical research center on Day 5 (approximately 96 hours after drug administration) upon satisfactory recovery of radioactivity. If the criteria for discharge are not met on Day 5, subjects will be required to remain confined for a maximum of 3 additional days (Days 6 to 8) until the criteria are met (daily check by quick counts or normal counts, as feasible). The in-house period should be prolonged up to the morning of Day 8 if at least 1 of the following applies:

- Total radioactivity in plasma is higher than 5% of radioactivity-Cmax and/or PK parameters for determination of the total radioactivity-elimination phase cannot be determined reliably.
- The mass balance in urine and feces is not complete by Day 5 (ie, >90%).
- The combined urinary and fecal excretion is not ≤1% of the administered dose per 24 hours for 2 consecutive days based on C-radioactivity “quick counts” or normal counts, as feasible.

If the criteria for discharge are still not met on Day 8, subjects may be discharged from the clinical site upon discretion of the Investigator. To ensure that adequate consideration is given to the protection of the subject's interests, subjects with an incomplete mass balance on Day 8 will be asked to return to the clinical site for one or two 24-hour visits (Day 11-12 and Day 15-16).

On the day of study drug administration (Day 1), an FDA-recommended high-fat (or a standardized breakfast, if applicable, as outlined in Section 3.4.4 and Section 3.4.7) with calculated caloric content will be provided.

Assessments during the treatment period will be performed as presented in the schedule of assessments (Table 1).

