The study will consist of a screening period (Day -21 to -2), a baseline period (Day -1), a single dose treatment on Day 1 with a minimum of 96 hours (=4 days) post dose in-house observation period (Days -1 up to afternoon Day 5), and a follow-up visit 30 days ( $\pm$ 2 days) after the [C]BTZ-043 dose. The subjects will be admitted to the clinical site on Day -1, at least 17 hours before the administration of [C]BTZ-043 for baseline evaluation. Subjects will be administered a single 500 mg [C]BTZ-043 dose as drinking suspension. Subjects will be confined to the clinical site for at least 96 hours following drug administration (ie, afternoon of Day 5). During this time, blood, feces, and urine samples for measurement of [C]BTZ-043 and metabolites will be collected. The radioactivity excreted in urine and feces as well as radioactivity in blood and plasma should be measured and the data should be communicated daily to [name] or his designee. The subjects will be released from the clinic approximately 96 hours to 168 hours after dose administration and upon satisfactory recovery of radioactivity (at least 90%) approved by the Sponsor's scientific advisor after consultation of the Sponsor. This will depend on the radioactivity excretion balance as assessed by a normal counting method or real time rapid analysis on site ('quick counting' procedure, utilizing liquid scintillation counter, or sample combustion apparatus) of radioactivity in plasma, urine, and feces accumulated until 96 hours, as feasible. The data has to be available before subjects will be released from the clinic.

The in-house period should be prolonged up to the morning of Day 8 if at least 1 of the following applies:

- Total radioactivity in plasma is higher than 5% of total radioactivity-Cmax and/or PK parameters for determination of the total radioactivity-elimination phase cannot be determined reliably.
- The mass balance in urine and feces is not complete by Day 5 (ie, <90%).
- The combined urinary and fecal excretion is not  $\leq$ 1% of the administered dose per 24 hours for 2 consecutive days based on C-radioactivity "quick counts" or normal counts, as feasible.

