AE=adverse event; BMI=body mass index; ECG=electrocardiogram; HBsAg=hepatitis B surface antigen; HCV=hepatitis C virus; PCR=polymerase chain reaction; PK=pharmacokinetic(s)

a Subjects will be in the clinic from Day -1 (predose) until Day 5 with possible extension (Day 6 to Day 8) as well as possible 24-hour visits (Day 11-12, Day 15-16). The 2 back-up subjects will stay in the clinic until the morning of Day 2.

b Subjects will be released from the clinic 96 hours after dose administration and upon satisfactory recovery of radioactivity.

c Complete physical examinations will be conducted at screening, Day -1, and follow-up/early termination. Symptom driven physical examinations may be conducted at any time, per the investigator's discretion.

d Sampling of nasal and throat mucosal cells. If deemed necessary, additional tests may be conducted during the study. The nonclinical project manager will be informed immediately upon availability of Day 11 results, as this will qualify the feces samples for metabolite profiling with regard to potential COVID-19 infectivity.

e Clinical laboratory tests (including clinical chemistry, hematology, and urinalysis): at screening; on Day -1 (admission), Day 2, and Day 4; and at follow-up.

f 12-lead ECG: at screening; Day -1 and 1 hour, 4 hours, and 24 hours postdose; at discharge; and at follow-up.

g Vital signs (supine systolic and diastolic blood pressure, pulse, body temperature, and respiratory rate): at screening; at admission; at predose and at 1 hour, 4 hours, and 24 hours postdose; at discharge; and at follow-up.

h Plasma sampling for PK of BTZ-043 and main metabolites in plasma, at predose and 0.25, 0.5, 1, 1.5, 2, 3, 5, 8, 12, 16, 24, 36, and 48 hours postdose.

i Total radioactivity in whole blood and plasmal: at predose and 0.25, 0.5, 1, 1.5, 2, 3, 5, 8, 12, 16, 24, 36, 48, 72, and 96 hours postdose (in case total radioactivity recovered is still <90%: in addition 120, 144, and 168 hours postdose and at further 24-hour visits [264 and 360 hours postdose until study completion]). Metabolite profiling in plasma, at predose and 0.25, 0.5, 1, 1.5, 2, 3, 5, 8, 12, 16, 24, 36, 48, 72, and 96 hours postdose (in case total radioactivity recovered is still <90%: in addition 120, 144, and 168 hours postdose).

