j Urine collection and pooling for BTZ-043 and main metabolites, total radioactivity, and metabolite profiling: at predose (within 12 hours prior to dosing) and over 0-24, 24-48, 48-72, and 72-96 hours postdose collection intervals (in case total radioactivity recovered is still <90%, in addition 96-120, 120-144, and 144-168 hours postdose and at further 24-hour intervals [Day 11-12 and Day 15-16] until study completion).

k Feces collection for total radioactivity and metabolite profiling; predose feces collection to be collected at any time within 48 hours prior to study drug administration (at home or in the clinic). After administration of BTZ-043, feces will be collected in 24 hour collection intervals up to 96 hours postdose (in case total radioactivity recovered is still <90%: in addition 120, 144, and 168 hours postdose and at further 24-hour intervals [Day 11-12 and Day 15-16] until study completion).

l If produced, vomit will be collected up to 8 hours after the administration of the study drug for total radioactivity determination.

m Day 6-8 procedures will only be conducted in case that the recovery of radioactivity was not satisfactory until Day 5. 24-hour visits procedures will only be conducted in case that the recovery of radioactivity was not satisfactory until Day 8. For the 24-hour visits (if applicable): feces collection to be collected at home within 48 hours prior to admission.

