5.0 Study Design

This study is a Phase 1, single-center, open-label study to investigate the absorption, metabolism, and excretion of BTZ-043 after a single oral administration of 500 mg BTZ-043 containing 3.7 MBq of [¹⁴C]BTZ-043 in 4 healthy adult male subjects.

A total of 4 evaluable subjects completing all procedures are required. Six (6) subjects will be enrolled in the cohort in order to have 4 evaluable subjects. If the cohort of 4 subjects administered with 500 mg BTZ-043 containing 3.7 MBq of [¹⁴C]BTZ-043 leads to less than 4 evaluable subjects, the 2 back-up subjects can be dosed subsequently to ensure that 4 subjects have completed all study procedures and are evaluable. If any of the 4 subjects vomits within 4 hours after study drug administration (approximately 2 times the median T_{max} of BTZ-043), the subject will be replaced.

Subjects will be admitted to the clinical research center on Day -1, which is the day prior to Day 1, the day of drug administration.

Subjects will receive a single oral dose of 500 mg BTZ-043 containing 3.7 MBq of [¹⁴C]BTZ-043 on Day 1. Subjects will be discharged from the clinical research center on Day 5 (approximately 96 hours after drug administration) upon satisfactory recovery of radioactivity. If the criteria for discharge are not met on Day 5, subjects will be required to remain confined for a maximum of 3 additional days (Days 6 to 8) until the criteria are met (daily check by quick counts or normal counts, as feasible). The in-house period should be prolonged up to the morning of Day 8 if at least 1 of the following applies:

- Total radioactivity in plasma is higher than 5% of radioactivity- C_{max} and/or PK parameters for determination of the total radioactivity-elimination phase cannot be determined reliably.
- The mass balance in urine and feces is not complete by Day 5 (i.e., <90%).
- The combined urinary and fecal excretion is not $\leq 1\%$ of the administered dose per 24 hours for 2 consecutive days based on ¹⁴C-radioactivity “quick counts” or normal counts, as feasible.

If the criteria for discharge are still not met on Day 8, subjects may be discharged from the clinical site upon discretion of the Investigator. To ensure that adequate consideration is given to the protection of the subject's interests, subjects with an incomplete mass balance on Day 8 will be asked to return to the clinical site for one or two 24-hour visits (Day 11-12 and Day 15-16).

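### Section 3.1.3 prints the recovery criterion with its inequality reversed, and Table 1 schedules no samples after 96 h for subjects held or recalled with at least 90% recovered

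*Protocol*

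**What the plan says.** **The prolongation rule.** Section 3.1.3 keeps a subject in-house up to the morning of Day 8 if any one of three criteria applies:

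- Plasma: total radioactivity is above 5% of its Cmax, or the elimination phase cannot be determined reliably.
- Recovery: printed as "The mass balance in urine and feces is not complete by Day 5 (ie, >90" percent.
- Excretion rate: combined urine and feces output is not at or below 1% of dose per 24 h on two consecutive days.

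The synopsis (Design and Treatments) prints the recovery criterion as "The mass balance in urine and feces is not complete by Day 5 (ie, <90" percent, and SAP Section 5.0 as "The mass balance in urine and feces is not complete by Day 5 (i.e., <90" percent. The synopsis also describes satisfactory recovery as at least 90%.

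**The recall rule.** Under the synopsis, a subject is asked back for Days 11-12 and 15-16 if, on Day 8, recovery is below 90% and/or excretion exceeds 1% per 24 h. Section 3.1.3 refers to an incomplete mass balance on Day 8 without repeating that definition.

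**The sampling rule.** Section 3.1.3 states: "Assessments during the treatment period will be performed as presented in the schedule of assessments". Table 1 footnote i (blood and plasma) adds late samples "in case total radioactivity recovered is still <90%: in addition 120, 144, and 168 hours postdose". Footnote j (urine) adds collections "in case total radioactivity recovered is still <90%, in addition 96-120, 120-144, and 144-168 hours postdose". Footnote k (feces) carries the same condition. Footnote m says "Day 6-8 procedures will only be conducted in case that the recovery of radioactivity was not satisfactory until Day 5", with a parallel condition for the return visits. SAP Appendix 2 repeats these footnotes.

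**The concern.** The body text of a discharge criterion contradicts the synopsis and the SAP. Read literally, it holds a subject for having recovered enough.

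The sampling trigger has the larger consequence. There are three grounds for keeping a subject and two for recalling him, but only recovery below 90% generates samples. Someone kept because "PK parameters for determination of the total radioactivity-elimination phase cannot be determined reliably" has no 120, 144 or 168 h blood sample scheduled with which to determine it. Someone held or recalled because he is still excreting has no scheduled collection to measure it.

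Mass balance and total-radioactivity pharmacokinetics are primary objectives. SAP Section 15.2.3 sets excretion to zero for intervals without a sample and, where needed, carries the last cumulative value forward, so such a subject's mass balance could stay at its 96 h value. SAP Section 15.2.2 reports a half-life as not calculable unless there are at least 3 numeric points and r² is at least 0.9025. A healthy volunteer would bear longer confinement or extra visits without the scheduled data that justify them.

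**Working it through.** **1. The plan's own counts.** Footnote i lists predose plus 15 times to 96 h, which is 16 samples. Adding 120, 144 and 168 h gives 19, and adding 264 and 360 h gives 21. These match the maxima in Protocol Table 3: 21 for total radioactivity in each of plasma and whole blood, and 19 for profiling. The volume also reproduces: 14×2 + 21×4 + 21×1 + 19×15 + 14 + 12 + 5 = 449 mL.

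**2. Hold, recall and sampling rules side by side.** The recall column assumes the same status on Day 8.

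| Recovery | Plasma criterion applies | Excretion criterion applies | Held: synopsis, SAP | Held: 3.1.3 as printed | Recalled | Samples after 96 h in Table 1 |
|---|---|---|---|---|---|---|
| 85% | no | no | yes | **no** | yes | yes |
| 92% | no | no | no | **yes** | no | no |
| 92% | yes | no | yes | yes | no | **no** |
| 92% | no | yes | yes | yes | yes | **no** |
| 92% | yes | yes | yes | yes | yes | **no** |

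The first two rows show the misprint. The last three show the sampling gap: such a subject has 16 scheduled radioactivity samples, the last at 96 h, and no excreta interval afterwards.

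**3. Is the gap realistic?** Assume first-order excretion, with cumulative recovery F(1 − e^(−kt)) and F between 92% and 100% of dose. A subject just reaching 90% at 96 h excretes 3.2% (F = 92%) to 7.8% (F = 100%) of dose in 72-96 h. He fails the 1% criterion with 2 to 10% of dose outstanding.

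**4. Size for excreta.** The documents give no tail rate or terminal half-life, so these are assumptions. Let 72-96 h excretion be 1% of dose, declining with half-life h. The previous day is then 2.0, 1.4 or 1.3% for h = 24, 48 or 72 h, so the two-day rule is not met.

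- Amount after 96 h = 1% / (2^(24/h) − 1)
- Part falling in 96-168 h = that amount × (1 − 2^(−72/h))
- Shift in a four-subject mean from one such subject = amount after 96 h / 4

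| h | After 96 h (% of dose) | Of which 96-168 h | Shift in mean (points) |
|---|---|---|---|
| 24 h | 1.00 | 0.88 | 0.25 |
| 48 h | 2.41 | 1.56 | 0.60 |
| 72 h | 3.85 | 1.92 | 0.96 |

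With at least 90% recovered, at most 10% of dose remains, so the ceiling is 10/4 = 2.5 points.

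**5. Size for plasma AUC.** Assume C(t) = A·2^(−t/6) + B·2^(−t/s), with C(0) = 1 standing in for Cmax, a fast half-life of 6 h and terminal half-life s. Put the curve at 5% of Cmax at 96 h, so B = 0.05·2^(96/s) and A = 1 − B. Total AUC = (6A + sB)/ln 2. The extrapolated share at 96 h is 0.05s/(6A + sB). At 168 h it is that share × 2^(−72/s).

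| s | A | B | Extrapolated at 96 h | Extrapolated at 168 h |
|---|---|---|---|---|
| 24 h | 0.200 | 0.800 | 1.2/20.4 = 5.9% | 0.7% |
| 48 h | 0.800 | 0.200 | 2.4/14.4 = 16.7% | 5.9% |
| 72 h | 0.874 | 0.126 | 3.6/14.3 = 25.1% | 12.6% |

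Only the slowest case crosses the 20% level at which SAP Section 15.2.2 flags parameters.

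**The case against.** **The misprint is harmless.** The bracket can be read as explaining what complete means, and no site would hold a subject because recovery succeeded. The risk of misuse is indeed low. The printed text still conflicts with two other statements of the same rule.

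**Collection is implied.** Section 3.1.3 refers to a daily check by counts during Days 6 to 8, and the synopsis calls for daily reporting of radioactivity in urine, feces, blood and plasma. The criteria cannot be checked without samples. SAP Section 15.2.3 also plans cumulative excretion to Days 12 and 16 for subjects with an incomplete mass balance. This stands in part: some collection would probably happen. But no text names a time point or interval after 96 h for these subjects, and Section 3.1.3 defers to Table 1.

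**Footnote m is broader.** Unsatisfactory recovery could be shorthand for all the discharge criteria. Even so, footnotes i to k state the 90% condition explicitly.

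**Extra blood is already allowed.** Section 3.5.1.3 permits more samples up to 500 mL. That is discretionary and schedules nothing.

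**The half-life argument is weak.** There are 15 postdose samples to 96 h, seven of them from 12 h onward, so three numeric points will rarely be lacking. Samples after the values fall below quantification would not help. This largely stands: the likelier gain is a better fit and less extrapolation, and nothing in the documents shows that the fit would fail.

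**Late profiling is not needed at 90% recovery or more.** This is fair, and the change can leave profiling on its present trigger.

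**Conclusion.** Both parts hold. The sign in Section 3.1.3 is wrong, and the intended reading is clear. The sampling footnotes cover only one of the three grounds for holding a subject and one of the two for recall, so a site following Table 1 as written would not schedule the samples the longer stay or the visit is meant to obtain.

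The size is modest. The excreta and AUC figures rest on assumed half-lives and an assumed tail rate; the 2.5-point ceiling follows from the 90% threshold and four subjects alone. The analysis is descriptive, and parameters with more than 20% extrapolation are flagged, not excluded. The correction is worth making because primary objectives are affected and it costs little, not because the study's conclusions are likely to change.

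**What to change.** - In Section 3.1.3, change the sign in the recovery criterion to *<90%*.
- In Table 1 footnotes i, j, k and m, and in SAP Appendix 2, replace the recovery condition with *if the stay is prolonged or the subject is recalled*.
- Carry the synopsis definition of incomplete mass balance on Day 8 into Section 3.1.3 and SAP Section 15.2.3 by reference. Leave the recall rule itself unchanged unless the sponsor intends otherwise.

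**Cost.** Wording in one protocol amendment and the SAP, with no added confinement or visits. The Table 3 maximum stays at 449 mL. Newly covered subjects give more blood: 3 × (4 + 1 + 15) = 60 mL for the in-house times, plus 2 × (4 + 1) = 10 mL if recalled for both visits. Their total rises from 449 − 70 = 379 mL to 439 or 449 mL, under the 500 mL limit. If plasma profiling stays tied to recovery below 90%, the three in-house times cost 3 × (4 + 1) = 15 mL.
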